5.0 TIME AND EVENTS TABLE

5.1 Time and Events Table

	Pre-study	Baseline assessment (T0)	Randomization Day 0	3-Week Follow-Up (T1)	6-Week Follow-Up (T2)

		Day 0		Day 21 (\pm 14)	Day 42 (\pm 14)
EMR eligibility screening	X				
Oncology clinician approval	X				
Informed consent and enrollment	X				
Survey outcome assessments		X		X	X
Study group assignment			X		
Semi-structured interview					X
EMR abstraction		X		X	X

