4.0 STUDY PLAN

4.1 Schema

This is a two-arm, randomized controlled trial of 40 patients with cancer who are parents of minor children. Participants will be approached in hospital or clinic settings, complete

baseline assessments, randomized to intervention (FACT) vs. control (waitlist control), and complete follow-up assessments 3-weeks post-randomization and 6-weeks post-randomization. Study visits will occur at NCCH, via telephone, or secure video. We anticipate enrolling participants over a six-month period and that active participation will last for a 2-month period.

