4.3.2.4 Control arm (Waitlist control)

Participants in the waitlist control condition will receive their usual care – which includes access to the UNC CCSP (for which the PI serves as the Deputy Director of Clinical Operations) by clinician- or self-referral. A waitlist control model allows the research team to collect maximally rigorous data while addressing the ethical considerations of completely withholding the study intervention from participants assigned to this arm.

These individuals will participate on the same schedule as the treatment arm but receive the study intervention after their data collection activities are complete. Given the elevated psychological distress that parents with cancer experience and the low risk profile of the protocol, use of a waitlist control group is appropriate.

4.3.2.5 3-Week Follow-up assessment (T1)

Participants will complete follow-up surveys via secure REDCap link or pen-and-paper.

4.3.2.6 6-Week Follow-up assessment (T2)

Participants will complete follow-up surveys via secure REDCap link or pen-and-paper.

The post-intervention semi-structured interview may be conducted in person at NCCH, by telephone, or by secure video. The interview content will ask participants to discuss barriers and facilitators to intervention use, desired communication content areas not addressed in the current communication tool (treatment arm only), feedback on their experiences communicating with their children, opinions on study procedures, suggestions for improvement to the intervention and/or study activities, and any psychosocial follow-up needs. The interview is expected to last approximately 30 minutes and will be conducted by a member of the study team with training in conducting such research interviews with patients. Participants are not required to answer questions they find emotionally distressing and are reminded of this right prior to beginning the interview. All interviews will be audiotaped and then transcribed for analysis.

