4.3.5.6 Patient Health Questionnaire – 2 (PHQ-2)

The PHQ-2 is a brief, well-validated measure of severity of depression symptoms and is used extensively in clinical and research settings (Appendix E).¹⁴ Participants are asked to respond to 2 items, respectively measuring depressed mood and anhedonia, and indicate the extent to which they were bothered by that symptom in the two weeks prior to the questionnaire. Items are Likert-type and have response options of 0 ("not at all"), 1 ("several days"), 2 ("more than half the days"), and 3 ("nearly every day"). The estimated time to complete this measure is no more than 1 minute.

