7.3 Data Analysis Plans

7.3.1 Evaluate acceptability of the intervention

To evaluate acceptability of the intervention, we will administer a satisfaction assessment to each participant after each follow-up study visit (T1 and T2) and conduct post-intervention interviews at T2. We will report the acceptability rate at T1, along with an exact 95% confidence interval.

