7.3.3 Evaluate feasibility of the intervention

To evaluate feasibility of intervention, we will report the percentage of patients who are approached about the study who:

- Enroll in the intervention (percent approached)
- Complete the intervention at each time point (percent completed per visit and overall)

We will also use descriptive statistics to assess the demographic characteristics of patients who enter, remain in, and drop out of the study. Comparisons will be made using Wilcoxon Rank sum tests for continuous characteristics and Fisher's Exact tests for categorical characteristics.

In addition, we will evaluate feasibility of study procedures including:

- Number of patients screened each month
- Number of contacts necessary to enroll participants and schedule follow-up appointments
- Proportion of completed study measures at each visit

Although adverse events are unlikely, we will examine the procedures for adverse event reporting and the study teams' response should this occur.

We will use qualitative analyses of the semi-structured interview data to explore barriers and facilitators to participation, including reasons for enrollment, non-participation (e.g. fears of unintended outcomes, competing demands, etc.), ineligibility, or withdrawal and use this information to refine study procedures in preparation for a larger-scale study.

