7.3.4 Explore impact of intervention on target outcomes

We will report on changes in CSES scores from pre- (T0) to post-intervention (T1, T2) . This pilot study is not designed nor powered to detect differences as the primary objectives are to evaluate the acceptability and feasibility of the intervention as compared to treatment as usual.

We will also report on changes in other patient-reported outcomes of interest including GAD-7 and PHQ-2 scores.

We will use descriptive statistics to report on the percentage of patients who engage in any communication behaviors about cancer with their children, the depth of their discussion, and their assessments of how their children responded to these conversations.

Data from this study will be used for preliminary estimates (for which the CSES will be the primary outcome measure) to power a future R01 testing the intervention. The projected effect size will be based on mean differences in SD for the CSES from this pilot study.

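### Do the overlapping T1 and T2 survey windows need a minimum gap between the two surveys?

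*Combined protocol and SAP*

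**What the plan says.** Section 4.1 counts both follow-ups from randomization: participants "complete follow-up assessments 3-weeks post-randomization and 6-weeks post-randomization". The table in 5.1 gives the tolerances. The column headed "3-Week Follow-Up (T1" is Day 21 plus or minus 14 days, and the column headed "6-Week Follow-Up (T2" is Day 42 plus or minus 14 days. Neither section states a minimum interval between the two surveys.

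For the waitlist arm, 4.3.2.4 says "These individuals will participate on the same schedule as the treatment arm".

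Three analyses use these visits:

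- Section 7.3.1, acceptability: "We will report the acceptability rate at T1, along with an exact 95% confidence interval".
- Section 7.3.3, feasibility, which includes "Proportion of completed study measures at each visit".
- Section 7.3.4, exploratory outcomes: "We will report on changes in CSES scores from pre- (T0) to post-intervention (T1, T2". It adds changes in GAD-7 and PHQ-2 without naming visits, and says that the CSES result will inform the effect size for a later trial.

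On the PHQ-2, 4.3.5.6 says that respondents "indicate the extent to which they were bothered by that symptom in the two weeks prior to the questionnaire".

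**The concern.** The plan presents two distinct follow-up times, yet a survey done on Day 30 fits either one. A participant could complete T1 and T2 on the same day within the table's limits, and the results would be reported as a 3-week and a 6-week change. Two PHQ-2 surveys less than 14 days apart also ask about some of the same days.

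CSES is where this could matter most, because 7.3.4 carries the pilot result into the effect size for the next trial. If the two CSES changes are not clearly tied to 3 and 6 weeks, the planners of that trial would have a less certain idea of when any effect appears.

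**Working it through.** **Inputs.** Targets Day 21 and Day 42, tolerance 14 days (5.1); time counted from randomization (4.1); T0 on Day 0 (5.1); two-week PHQ-2 recall (4.3.5.6); n = 20 for the acceptability interval (7.2).

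**Windows.** T1: 21 - 14 = 7 to 21 + 14 = 35. T2: 42 - 14 = 28 to 42 + 14 = 56. Each has 29 days. They share Days 28-35, which is 8 days. With T1 first, the gap can run from 0 to 56 - 7 = 49 days, against a nominal 21.

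**Permitted day pairs.** The number of pairs with gap g is 29 - |g - 21|.

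- All pairs: 29 × 29 = 841. Pairs with T2 before T1 (g from -7 to -1): 1 + 2 + ... + 7 = 28. This leaves 813.
- Same day (g = 0): 8.
- Gap 0-13 days: 8 + 9 + ... + 21 = 203.
- Gap of 14 days or more: 813 - 203 = 610.

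These count what the table allows. They do not predict visits, and staff who schedule near the targets will rarely produce short gaps.

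**Which planned results depend on the gap?**

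| Planned result | Uses the T1-to-T2 gap? |
|---|---|
| Acceptability rate and exact interval (7.3.1) | No; T1 only |
| Completion at each visit (7.3.3) | No; counts completed measures, whatever the spacing |
| CSES change from T0 (7.3.4) | No; each change is taken from T0 |
| GAD-7 and PHQ-2 changes (7.3.4) | No T1-versus-T2 contrast is stated |
| Comparison between arms | No; same schedule in both arms |

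The precision figure in 7.2 reproduces: the exact interval for 15/20 is 50.9% to 91.3%, and the largest half-width at n = 20 is 22.8 points, within the stated 23. The timing of T2 does not enter it.

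**Would a 14-day minimum gap help?** The figure would come from the PHQ-2 recall period.

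- *Labels.* T1 could still fall anywhere on Days 7-35 and T2 anywhere on Days 28-56. One participant's T1 on Day 35 and another's T2 on Day 28 would both remain valid, so summaries at each visit keep the same overlap. The looseness comes from the 14-day tolerance, not from the missing gap.
- *Recall.* Shared recall between T1 and T2 touches no planned contrast. Shared recall between T0 and T1 does, and it arises for T1 on Days 7-13 (7 of 29 days). The gap rule leaves that untouched.
- *Cost.* The earliest T2 day becomes the later of Day 28 and T1 + 14. The rule binds for T1 on Days 15-35 (21 of 29 days).

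| T1 day | Permitted T2 days under the rule | Number, of 29 |
|---|---|---|
| 14 | 28-56 | 29 |
| 21 | 35-56 | 22 |
| 28 | 42-56 | 15 |
| 29 | 43-56 | 14 |
| 35 | 49-56 | 8 |

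For T1 on Days 29-35 (7 of 29 days), a survey on Day 42 would become a deviation, and T2 would be pushed later than six weeks. The semi-structured interview also takes place at T2, and 2.1 makes interview data part of how acceptability is defined. The rule would therefore shorten the time available for something the primary objective needs.

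**The case for a change.** The best case for a change is that it is cheap and that CSES has a use beyond this trial. A footnote and a reminder date would stop same-day surveys. Staff who already schedule near target would lose nothing. Data from early T2 surveys could be kept, and 8.4.3 already provides for recording deviations. With T1 exactly on Day 21, a T2 on Days 28-34 is permitted and shares PHQ-2 recall days with it, so the issue does not need extreme scheduling. If completion days were independent and uniform within each window, which the documents do not say, (203 + 28)/841 = 27% of pairs would be under 14 days apart, including those in reverse order.

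Part of this stands. The arithmetic is right, and the 3-week and 6-week labels are approximate. Section 7.3.4 also does not say which visit supplies the CSES effect size, but that would be so with any windows.

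The remedy does not follow. The 14-day figure belongs to the PHQ-2, whereas the stated worry is CSES, which 4.3.5.7 describes as a rating of confidence with no recall period. A 7-day minimum would at least leave Days 42-56 for a T1 on Day 35, but it too would leave both windows, and hence the labels, as they are.

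**Conclusion.** No change to the plan is needed. The windows overlap by 8 days and no minimum gap is set, but the consequence is confined to the time labels of exploratory, unpowered changes from baseline. No effect is shown on the acceptability rate, its interval, completion at each visit or the comparison between arms, and the documents give no figures from which an effect on CSES could be sized. Wide windows for patients under treatment for cancer are a fair trade-off in a feasibility pilot, and a spacing rule would take days from T2 with little or no gain for any planned result.

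What remains is ordinary reporting practice: give the actual assessment days beside the T1 and T2 results and read the CSES changes against them. This assumes that completion dates are available for paper as well as online surveys, and that each survey is assigned to the visit for which it was issued. Table 1 in 4.3.5 supports the second assumption, since the resource-use item is given at T2 but not at T1. The conclusion also rests on there being no T1-versus-T2 contrast. If one were added, spacing would deserve a fresh look.

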6.0 UNANTICIPATED PROBLEMS

6.1 Definition

As defined by UNC's IRB, unanticipated problems involving risks to study participants or others (UPIRSO) refers to any incident, experience, or outcome that:

- Is unexpected (in terms of nature, severity, or frequency) given (a) the research procedures that are described in the protocol-related documents, such as the IRB-approved research protocol and informed consent document; and (b) the characteristics of the participant population being studied;
- Is related or possibly related to a participant's participation in the research; and
- Suggests that the research places participants or others at a greater risk of harm (including physical, psychological, economic, or social harm) related to the research than was previously known or recognized.

6.2 Reporting

Any UPIRSO that occurs during the conduct of this study and that meets all three criteria listed in 6.1 must be reported to the UNC IRB using the IRB's web-based reporting system.

7.0 STATISTICAL CONSIDERATIONS

7.1 Study Design

This is a two-arm pilot RCT testing the acceptability, feasibility, and preliminary evidence of efficacy for a novel communication intervention for parents with cancer.

The primary objective of acceptability will be measured using the 6-item satisfaction survey. Total scores range from 0-18, so a score of 12 or higher will be considered "acceptable". If the percentage of patients who report the intervention is acceptable is 75% or higher, the intervention will be considered for future testing.

7.2 Sample Size and Accrual

We will recruit 55 patients over 6 months for the proposed study, with the hope of at least 20 patients completing T1 measures. A 95% exact binomial confidence interval (CI) will

be reported for the acceptability rate (only in the intervention group), and with n=20, the CI will have precision no more than +/- 23%. If the rate is 75%, the CI will be 50.9%, 91.3%).

For qualitative interview data, sample size estimation is based on projections of the number of participants needed to reach saturation of the concept. The sample size for the proposed study is adequate for qualitative analysis and consistent with psychosocial intervention development.^{18,19}

We are confident we have adequate access to the proposed sample during the study time frame. In 2019, NCCH records included 522 English-speaking adults ages 22-54 years with a stage IV solid tumor. Our screening records suggest ~60-70% NCCH patients in this age range are parents of minor children. Data from epidemiologic studies indicate that an estimated 30% of all adult breast cancer patients are parents of minor children.¹

Based on the PI's other research studies with parents with cancer, we conservatively expect to recruit, consent, and enroll ~10 patients/month for six months. The number of eligible patients per month is higher, however we consider factors that typically lead to deferred enrollment/consent such as patient fatigue, clinic scheduling delays, and intervening medical events.

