1.0 BACKGROUND AND RATIONALE

1.1 Study Synopsis

This is a single center, two-arm pilot randomized controlled trial (RCT) evaluating the feasibility and acceptability of a novel psychosocial intervention, Families Addressing Cancer Together (FACT) delivered as a mobile response web application (mobile web app). FACT is a theory-guided, psychoeducational intervention designed to improve parents' confidence and ability to talk about their cancer with their minor children. We will enroll 40 patients with cancer who have a minor child to participate in this 6-week study. The primary hypothesis being tested is that an intervention that assists parents with their communication needs with their children can be feasible, acceptable, and improve parental communication self-efficacy when compared with a waitlist control condition. Findings from this study will inform a future grant application to further test this intervention in a randomized full efficacy trial.

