4.3.2.2 Randomization

Participants will be randomized to one of two arms: (1) intervention arm, or (2) control arm. Participants will be assigned with an allocation ratio of 1:1 and stratified by disease status: advanced (stage IV or equivalent) vs non-advanced. This will be implemented through REDCap's randomization module which will directly follow entry of baseline data. Setup of the randomization module will be done only by the PI or CRC, and the study biostatistician will confirm that the randomization scheme logic is functional before any data is collected. This logic will be preserved such that group assignment cannot be altered or manipulated when accrual begins.

Given the nature of this study, a double-blind design is not possible as both the participants and recruiting staff will be able to easily infer group assignment.

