4.7 Removal of Patients from Protocol

Participants will be removed from the study when any of the criteria listed in Section 3.2 apply or the participant elects to withdraw from the study. If this occurs, the PI will be notified and the reason for study removal and the date the participant was removed will be documented in the Case Report Form.

In order to support the statistical integrity of analyses, the pre-randomization discontinuation of any participant will trigger the recruitment and enrollment of an additional participant. Participants who discontinue after randomization will not be “replaced” in this manner.

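### The protocol gives two unreconciled sample sizes, 40 and 55; if 40 are randomised 1:1, the n=20 behind the stated precision leaves no room for attrition

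*Combined protocol and SAP*

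**What the plan says.** Three sections of the combined protocol and SAP give the size of the trial.

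- Section 1.1 (Study Synopsis): "We will enroll 40 patients with cancer who have a minor child to participate in this 6-week study".
- Section 4.1 (Schema): "This is a two-arm, randomized controlled trial of 40 patients with cancer who are parents of minor children". The same section adds "We anticipate enrolling participants over a six-month period".
- Section 7.2, which justifies the sample size, states: "We will recruit 55 patients over 6 months for the proposed study, with the hope of at least 20 patients completing T1 measures". On accrual it says "we conservatively expect to recruit, consent, and enroll ~10 patients/month for six months".

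Section 7.2 then gives the precision of an exact 95% binomial interval for the acceptability rate in the intervention group only: "with n=20, the CI will have precision no more than +/- 23" percent, with an interval of 50.9% to 91.3% if the rate is 75%. Section 7.3.1 places this rate at T1, and Table 1 (section 4.3.5) gives the satisfaction scale to the treatment arm only.

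Two other rules determine how many participants can contribute. Section 4.3.2.2: "Participants will be assigned with an allocation ratio of 1:1", stratified by disease status. Section 4.7 replaces participants who discontinue before randomisation, but after it: "Participants who discontinue after randomization will not be" replaced.

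**The concern.** The totals of 40 and 55 both stand in current text, and no sentence relates them. Section 8.4 requires the study to be run as the protocol describes, which cannot be done with two totals. Staff working from sections 1.1 and 4.1 would stop 15 patients earlier than staff working from section 7.2. Retention, which is part of the secondary objective, also has no fixed planned denominator.

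The choice of total also decides whether the precision statement is attainable. It is written for 20 participants in one arm at a follow-up visit. Half of 40 is already 20 before anyone is lost.

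**Working it through.** **Inputs.** Total of 40 (sections 1.1, 4.1) or 55 (7.2); 1:1 allocation (4.3.2.2); FACT arm only, n=20, exact 95% interval (7.2); T1 (7.3.1); no replacement after randomisation (4.7); six months of accrual (4.1, 7.2) at about 10 per month (7.2). The documents give no attrition rate, so 5-30% is an assumed range.

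**1. The plan's own figures.** The Clopper-Pearson limits for x of n are the 2.5% quantile of Beta(x, n−x+1) and the 97.5% quantile of Beta(x+1, n−x). Half-width is (upper − lower)/2.

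- 15/20: 50.9% to 91.3%, as stated.
- Largest half-width at n=20, which occurs at 10/20: (72.8 − 27.2)/2 = 22.8 points. The plan's 23 is correct when read as a half-width.

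**2. Attrition that n=20 tolerates.** The formula is 1 − 20/(FACT arm size).

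| Randomised | FACT arm | Tolerated attrition |
|---|---|---|
| 40 | 20 | 1 − 20/20 = 0% |
| 55 | 27 | 1 − 20/27 = 26% |
| 55 | 28 | 1 − 20/28 = 29% |

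**3. Chance of at least 20 FACT completers.** This is the upper tail of a binomial with the arm size and retention = 1 − attrition. For an arm of 20 it reduces to retention to the power 20.

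| Assumed attrition | Arm of 20 | Arm of 27 | Arm of 28 |
|---|---|---|---|
| 5% | 0.95^20 = 36% | >99% | >99% |
| 10% | 0.90^20 = 12% | >99% | >99% |
| 20% | 0.80^20 = 1% | 84% | 91% |

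**4. Precision if the FACT arm is 20.** Expected completers are 20 × (1 − attrition), that is 19 at 5% and 14 at 30%.

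| Completers | Worst-case half-width (points) | Half-width at the observed rate(s) nearest 75% (points) |
|---|---|---|
| 20 | 22.8 | 20.2 (15/20) |
| 19 | 23.3 | 21.0 (14/19) |
| 18 | 24.0 | 21.9 (13/18), 20.6 (14/18) |
| 17 | 24.6 | 21.5 (13/17) |
| 16 | 25.3 | 22.6 (12/16) |
| 15 | 26.1 | 23.7 (11/15) |
| 14 | 27.0 | 24.9 (10/14), 23.1 (11/14) |

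Losing one FACT participant takes the worst case past 23, though only just. Near the 75% threshold the half-width stays within 23 down to 16 completers.

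**5. Accrual.** 40/6 = 6.7 per month and 55/6 = 9.2 per month, against about 10 stated (10 × 6 = about 60). The rate sits closer to 55, but about 60 exceeds both totals.

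**6. Reading 55 as recruited and 40 as randomised.** This implies (55 − 40)/55 = 27% lost before randomisation, which no section states. The FACT arm would still be 20, so steps 2 to 4 for 40 apply unchanged.

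**The case against.** The best defence is that the totals count different things. Section 7.2 speaks of recruiting and section 1.1 of enrolling. The replacement rule in section 4.7 also gives a mechanism by which more people are recruited than randomised. This has some force, but section 4.7 gives no number, and the accrual sentence in section 7.2 treats recruiting, consenting and enrolling as one step. Even if the reading is right, the FACT arm has about 20 and still no attrition allowance.

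Other points stand in part:

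- Section 7.2 is coherent by itself: with 55 randomised, 20 FACT completers is a comfortable target. The attrition problem is therefore conditional on 40.
- No calculation in the plan is wrong. The precision statement is conditional on n=20 and remains true as such. The error is an inconsistency between totals.
- Attrition may be at the low end of the assumed range. T1 is a 10-15 minute survey at three weeks, with a 14-day window either side and a $20 payment. Even so, 5% attrition leaves only a 36% chance of 20 completers from 20.
- With stratified allocation and no stated block size, 40 randomised might not split exactly 20/20. The probabilities for 40 assume that it does.
- The accrual rate may show capacity rather than the intended target, so it is weak evidence for 55.
- This is a pilot, and the loss of precision is small. The need for correction therefore rests on the conflicting totals, with the attrition figures secondary.

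**Conclusion.** The concern holds. Sections 1.1 and 4.1 cannot both be followed alongside section 7.2, and the 15-patient gap is unexplained. This must be corrected because the enrolment target is a core design number.

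The consequence for precision depends on which total is meant. If 55 are randomised, the statement at n=20 is well supported. If 40 are randomised, it requires complete T1 follow-up in FACT, and over the assumed 5-30% attrition the worst-case half-width rises by about 1 to 4 points. The progression rule in section 7.1 uses the observed percentage against 75%, so it is unaffected. These results assume an even split and independent dropout at a common rate.

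**What to change.** State one randomised total in sections 1.1, 4.1 and 7.2, and add a sentence on how 40 and 55 relate (for example, recruited versus randomised). Then:

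- **If 55 are randomised:** change sections 1.1 and 4.1 to 55, with 27-28 per arm. The stated precision at n=20 can stay.
- **If 40 are randomised:** rewrite section 7.2 with an explicit T1 attrition assumption, the expected number of FACT completers and the matching worst-case half-width, for example 24.0 points at n=18 (10% attrition) or 25.3 at n=16 (20%).
- **In either case:** say that the target is at least 20 FACT-arm participants completing T1, since the present sentence names no arm.

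The cost is protocol wording. Keeping 40 also means publishing a slightly less favourable precision. The correction does not in itself require more patients.
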